7.4 Precautions Regarding Concomitant Medications

Refer to the following websites for updated lists of CYP inhibitors, inducers, and substrates:

- <http://www.fda.gov/Drugs/DevelopmentApprovalProcess/DevelopmentResources/DrugInteractionsLabeling/ucm093664.htm#potency>
- <http://medicine.iupui.edu/clinpharm/ddis/table.aspx>

8 SAFETY CONSIDERATIONS

Study assessments of safety include adverse events, clinical laboratory tests, physical examinations, and vital signs.

In the following sections, the sponsor's safety monitoring procedures are described (Section 8.1). Adverse events are discussed in detail in the context of patient management, study drug dose modification, and safety reporting requirements, including follow-up procedures (Sections 8.2 and 8.3). Clinical laboratory safety tests are presented

([Section 8.4](#)). The study procedures for physical examinations and vital signs are also provided ([Section 8.5](#)).

8.1 Safety Monitoring

The sponsor will periodically monitor safety data during the clinical study in addition to reviewing individual safety case reports, by examining the incidence and severity of adverse events and serious adverse events, changes in laboratory results, and other data (such as aggregate analysis of data from other enzalutamide studies). Any relevant safety concerns will be communicated to the investigators and regulatory agencies, as appropriate.

8.2 Special Safety Considerations

8.2.1 Study Drug Dose Modification Due to Adverse Event

The instructions for modifying the dose of study drug due to an adverse event are provided in [Section 6.2.4](#) for enzalutamide.

8.2.2 Overdose Management

The medical monitor must be contacted in the event of a study drug overdose.

An overdose is defined as any dose greater than the protocol-specified dose of enzalutamide 160 mg once daily. In the event of an overdose, treatment with study drug should be stopped and general supportive measures initiated, taking into consideration the half-life is 5.8 days for enzalutamide. Patients may be at increased risk of seizures following an overdose of enzalutamide. There is no known antidote to overdose.

All overdose events are to be reported as events of special interest within 24 hours of awareness by the study site according to [Section 8.3.5](#), whether or not the event meets adverse event criteria.

8.2.3 Contraception

A patient must use a condom if having sex with a pregnant woman. Patients must not donate sperm from first dose of study drug through 3 months after the last dose of study drug.

A patient and his female partner of childbearing potential must use 2 acceptable methods of birth control (1 of which must include a condom as a barrier method) from screening through 3 months after the last dose of study drug. The 2 acceptable methods of birth control are as follows:

1. A condom (barrier method is required)
AND
2. One of the following is required:

- Established and ongoing use of oral, injected, or implanted hormonal method by the female partner
- Placement of an intrauterine device or intrauterine system by the female partner
- Additional barrier method including contraceptive sponge or occlusive cap (diaphragm or cervical/vault caps) with spermicidal foam/gel/film/cream/suppository by the female partner
- Tubal ligation in the female partner performed at least 6 months before screening
- Vasectomy or other procedure resulting in infertility (eg, bilateral orchiectomy) performed at least 6 months before screening

8.3 Adverse Event Definitions and Reporting

8.3.1 Adverse Event Definitions

Definitions are provided in this section for adverse events, events of special interest, serious adverse events, treatment-emergent adverse events, suspected unexpected serious adverse reactions (SUSARs), and unexpected adverse events.

Adverse events: An adverse event is any unfavorable and unintended sign (including an abnormal laboratory finding), symptom, or disease temporally associated with the use of a study drug, whether or not related to the study drug.

Examples of adverse events include the following:

- A change, excluding minor fluctuations, in the nature, severity, frequency, or duration of a pre-existing condition
- Development of an intercurrent illness during the study
- Development of symptoms that may or may not be related to the use of a concomitant medication or investigational product
- Injury or accidents: if a medical condition is known to have caused the injury or accident, the medical condition and the accident should be reported as 2 separate medical events (eg, for a fall secondary to dizziness, both “dizziness” and “fall” should be recorded separately)
- Investigational abnormalities (eg, laboratory parameters, vital signs, ECG data) should be defined as adverse events only if the abnormality meets one of the following criteria:
 - Induces clinical signs or symptoms
 - Needs active intervention
 - Needs interruption or discontinuation of study medication
 - Abnormality or investigational value is clinically significant in the opinion of the investigator

An adverse event **does not** include the following:

- Medical or surgical procedures (eg, surgery, endoscopy, tooth extraction, transfusion); the condition that leads to the procedure is an adverse event
- Pre-existing diseases or conditions present or detected before the start of study drug administration that do not worsen
- Situations where an untoward medical event has not occurred (eg, planned hospitalization for an elective procedure as known at the time of informed consent)

Events of special interest: Adverse events of special interest are any events identified for intensive monitoring during the study. For MDV3100-18, events of special interest include overdose ([Section 8.2.2](#)) and pregnancy in the partner ([Section 8.3.7](#)).

Serious adverse events: Any adverse event that meets any of the criteria in Table 9 as determined by the investigator or sponsor.

Table 9: Criteria for Serious Adverse Events

Criterion	Comment
Results in death	Death is an outcome, not an adverse event. The primary adverse event resulting in the death should be identified.
Is life threatening (immediate risk of death from the adverse event as it occurred)	Does not include an event that hypothetically might have caused death if it were more severe.
Results in or prolongs an existing inpatient hospitalization	For hospitalizations for surgical or diagnostic procedures, the illness leading to the surgical or diagnostic procedure will be identified as the serious adverse event (not the procedure).
Results in persistent or significant incapacity or substantial disruption of the ability to conduct normal life functions	Permanent or substantial disruption of a person's ability to conduct normal life functions.
Results in a congenital anomaly/birth defect	
Important medical events which jeopardize the subject and may require medical or surgical intervention to prevent one of the outcomes listed above	Examples include drug-induced bronchospasm requiring intensive treatment in an emergency room or at home, blood dyscrasias or convulsions that do not result in inpatient hospitalization, and the development of drug dependency or drug abuse.

Source: US Code of Federal Regulations: 21 CFR 312.32 [75 FR 59961]

Treatment-emergent adverse events: Adverse events observed following administration of the study drug.

Suspected unexpected serious adverse reactions (SUSARs): Adverse events assessed as serious, related, and unexpected.

Unexpected adverse events: Adverse events for which the nature or severity is not consistent with the reference safety information.

8.3.2 Adverse Event Reporting

To elicit adverse event reports from patients, the study site personnel should question the patient in a general way without suggesting specific symptoms.

All patients who experience an adverse event will be evaluated at appropriate time intervals until the event resolves or stabilizes. At the conclusion of the study, the investigator and medical monitor will assess unresolved adverse events and determine if additional follow-up is warranted as described in [Section 8.3.6](#).

All adverse events, whether or not related to the study drug, must be fully and completely documented on the adverse event case report form and in the patient's clinical record. In addition, any adverse event resulting in permanent treatment discontinuation must be recorded on the treatment discontinuation case report form as well as documented in the patient's clinical record. Adverse event terms should include a diagnosis or underlying cause, as available, in preference to listing the individual signs and symptoms. If the diagnosis is not known, the investigator should record each sign and symptom as an individual adverse event.

8.3.2.1 Adverse Event Reporting Periods

Collection and reporting of adverse event information will begin at the time the patient signs informed consent for serious adverse events and from the first dose of study drug for nonserious adverse events, and will continue through 30 days after the last dose of study drug treatment or before initiation of cytotoxic chemotherapy, a lutamide (bicalutamide, nilutamide, or flutamide), or a new investigational therapy, whichever occurs first. Additional reporting instructions for serious adverse events and events of special interest are provided in [Section 8.3.5](#).

All adverse events from the time of the first dose of any study drug treatment must be documented on the adverse event case report form and in the patient's clinical record. Any event occurring during screening must be documented on the medical history case report form and in the patient's clinical record for any patient who subsequently meets eligibility criteria and proceeds to treatment.

8.3.3 Assessment of Causal Relationship

The investigator will assess the relationship of an adverse event to study drug according to the criteria in [Table 10](#) and document the relationship in the patient's source documents.

Adverse events considered in the relationship categories of "Possible" or "Probable" should be considered "adverse events whose relationship to the study drugs could not be ruled out."

Table 10: Criteria for Determining Causal Relationship to Study Drug

Relationship	Criteria
Not Related	A clinical event, including laboratory test abnormality, with a temporal relationship to drug administration that makes a causal relationship improbable, and/or in which other drugs, chemicals, or underlying disease provide plausible explanations.
Possible	A clinical event, including laboratory test abnormality, with a reasonable time sequence to administration of the drug, but that could also be explained by concurrent disease or other drugs or chemicals. Information on drug withdrawal may be lacking or unclear.
Probable	A clinical event, including laboratory test abnormality, with a reasonable time sequence to administration of the drug, unlikely to be attributed to concurrent disease or other drugs or chemicals, and that follows a clinically reasonable response on re-administration (rechallenge) or withdrawal (dechallenge).

8.3.4 Assessment of Severity (Intensity)

Severity describes the intensity of a specific adverse event (mild, moderate, or severe). The particular event may be of relatively minor medical significance (such as severe headache). Severity is not the same as “serious,” which is based on patient/event outcome or action criteria.

Investigators will grade the severity of adverse events according to the National Cancer Institute Cancer Therapy and Evaluation Program Common Terminology Criteria for Adverse Events (CTCAE), version 4. For terms not specified within the CTCAE, the criteria in Table 11 should be used to determine grade.

Adverse event severity should be recorded in the appropriate section of the adverse event case report form and in the patient’s source documents.

Table 11: Criteria for Determining the Severity (Intensity) of an Adverse Event

Grade	Intensity or Severity	Clinical Description
1	Mild	Asymptomatic or mild symptoms, clinical or diagnostic observations only; intervention not indicated
2	Moderate	Minimal, local, or noninvasive intervention indicated; limiting age-appropriate instrumental activities of daily living
3	Severe or medically significant	Not immediately life-threatening; hospitalization or prolongation of hospitalization indicated; disabling; limiting self-care activities of daily living
4	Life-threatening	Life-threatening consequences; urgent intervention indicated
5	Death	Death related to adverse event

Source: Common Terminology Criteria for Adverse Events v4.0

8.3.5 Serious Adverse Event and Event of Special Interest Reporting

Study site personnel will collect and record serious adverse events on the adverse event case report form from the time the patient signs the informed consent form through screen failure or 30 days after the last dose of study drug treatment or before initiation of cytotoxic chemotherapy, a lutamide (bicalutamide, nilutamide, or flutamide), or a new investigational therapy, whichever occurs first. Serious adverse events reported to the investigator after the safety reporting period should be reported to the sponsor if the investigator assesses the event as related to the study drug.

Using a serious adverse event report form, all serious adverse events and events of special interest must be reported **within 24 hours** of the study site personnel's knowledge of the event, regardless of the investigator assessment of the relationship of the event to study drug, to this contact:

Name: PPD [REDACTED]
Fax: PPD [REDACTED] (US)
Backup Fax: PPD [REDACTED] (United Kingdom)
Email: PPD [REDACTED]
Phone: PPD [REDACTED]

The initial report should include, at minimum, the following:

- Study number (MDV3100-18)
- Site name and number
- Investigator name
- Patient (study ID) number, sex, and age
- Details of study drug administration
- The date of the report
- A description of the serious adverse event or event of special interest (event term, seriousness of the event)
- Causal relationship to the study drug

If the patient died, the report should include the cause of death as the event term (with fatal outcome) and whether or not the death was related to study drug, as well as the autopsy findings if available.

8.3.5.1 Clarification in Reporting of Seizures

Seizure (convulsive or nonconvulsive) is always reported as a serious adverse event.

8.3.5.2 Clarification in Reporting of Deaths

Death is not an adverse event but is an outcome of an adverse event. For this protocol, reports of death without an adverse event will be managed as expedited reports (SUSARs) until the sponsor receives additional information.

8.3.5.3 Clarification in Reporting of Disease Progression as an Adverse Event

Disease progression is not unexpected in this study population and the term “disease progression” should not be reported as an adverse event unless a more specific clinical term is not defined or available. When clinical disease progression is identified, the clinical event that identifies the disease progression, if known, should be reported as the adverse event.

8.3.6 Follow-Up of Serious and Nonserious Adverse Events

All adverse events reported during the study should be followed at appropriate intervals until resolution, or until the event has stabilized, reached a new baseline, or (if enzalutamide is discontinued) a new antineoplastic treatment is initiated (all follow-up results are to be reported to the sponsor or designee).

Adverse events that remain unresolved at the conclusion of the study may continue to be monitored if warranted based on clinical assessment by the investigator and medical monitor.

Patients should be contacted by phone and written requests as appropriate for adverse event follow-up if they do not come to the clinic for safety follow-up as specified in [Section 5.4](#).

8.3.7 Pregnancy Reporting Procedure

If a study participant impregnates his partner following the first dose of study drug through 3 months after permanent discontinuation of study drug treatment, the study participant should report the pregnancy to the investigator. The investigator will report the pregnancy to the sponsor in the same timeframe as a serious adverse event ([Section 8.3.5](#)). The sponsor will provide forms to the investigator for use in reporting. The expected date of delivery or expected date of the end of the pregnancy, last menstruation, estimated conception date, pregnancy result, and neonatal data, etc, should be included in this information.

The investigator will follow the medical status of the mother, as well as the fetus, and will report the outcome to the sponsor.

8.4 Clinical Laboratory Safety Tests

Routine clinical laboratory safety tests (hematology, serum chemistry) will be performed according to the schedule of activities ([Appendix 2](#)), as will PSA and testosterone tests. Samples will be stored until the specified analyses are completed and then they will be destroyed in accordance with standard laboratory practice and applicable local regulations.

A list of the required routine clinical laboratory safety tests is provided in Table 12. All samples for laboratory analysis must be collected, prepared, labeled, and shipped according to laboratory requirements.

All clinical laboratory safety tests will be performed by the local laboratory specified in Form FDA 1572 Section 4. The local laboratory reference ranges will be used. Eligibility at screening will be based on local laboratory assessments.

A different clinical laboratory may be used for unscheduled visits or for urgent care. Such laboratory data will not be entered into the study database and these local laboratories will not be included on the FDA 1572 form.

Table 12: Clinical Laboratory Safety Tests

Hematology	Chemistry
Hematocrit	Albumin
Hemoglobin	Alkaline phosphatase
Mean corpuscular volume	ALT (alanine aminotransferase)
Platelet count	AST (aspartate aminotransferase)
Red blood cell count	Blood urea nitrogen and creatinine
White blood cell count with differential	Ca ⁺⁺
	Creatine phosphokinase
	Glucose
	Lactate dehydrogenase
	Magnesium, phosphate
	Na ⁺ , K ⁺ , total CO ₂ (bicarbonate), Cl ⁻
	Total bilirubin
	Total protein

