5.3 Permanent Treatment Discontinuation

Permanent treatment discontinuation is defined as cessation of study drug treatment administration. Safety follow-up will be performed per [Section 5.4](#).

Temporary treatment interruption is not considered permanent discontinuation. Regularly scheduled study visits will continue for patients based on their enrollment date when their treatment is interrupted any time and restarted.

The reasons that require patients to *permanently discontinue* study drug treatment are as follows:

- Adverse event or intercurrent illness: Any intolerable adverse event that cannot be ameliorated by the use of adequate medical intervention or that in the opinion of the investigator or medical monitor would lead to undue risk if study treatment were continued. Refer to [Section 8.3.1](#).
- Gross noncompliance with protocol: The medical monitor or investigator may request permanent treatment discontinuation in the event of a major protocol deviation, lack of cooperation, or noncompliance.
- Administration of prohibited concomitant therapy: Refer to [Section 7.2](#). NOTE: Patients who discontinue due to administration of a prohibited concomitant therapy will remain in the study and complete safety follow-up assessments per [Section 5.4](#).
- Laboratory abnormality defined as follows, unless the cause is identified and satisfactorily addressed, and the abnormality subsequently improves:
 - Creatinine > 354 µmol/L (> 4.0 mg/dL)
 - AST, ALT, or total bilirubin > 5-times the ULN
 - Absolute neutrophil count ≤ 750/µL
 - Platelet count < 50,000/µL
- Seizure: Regardless of resolution of any identified etiology.
- Death

- Loss to follow-up: Refer to [Section 5.5](#).
- Sponsor discontinuation of study: The sponsor reserves the right to terminate the study any time for any reason as described in [Section 13.6](#). The sponsor will terminate this study following completion of the study objectives, or earlier if deemed necessary.

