- [6] At investigator discretion (eg, significant bone pain or a skeletal-related event for ^{99m}Tc-MDP bone scintigraphy; or suspicion of soft tissue disease progression for CT or MRI) or (for ^{99m}Tc-MDP bone scintigraphy only) to coincide with NaF-3 unless bone disease progression was confirmed earlier. Progression at week 13 or earlier will require a confirmatory ^{99m}Tc-MDP bone scintigraphy at least 6 weeks later showing at least 2 additional new lesions related to prostate cancer (compared with the previous scan). After week 13, no confirmation of progression will be required if at least 2 new lesions related to prostate cancer are observed. If no bone disease progression was seen by ^{99m}Tc-MDP bone scintigraphy before NaF-3, then ^{99m}Tc-MDP bone scintigraphy will be required at the time of NaF-3. Send copies of bone scintigraphy images to the central imaging vendor for archiving.
- [7] Includes vital signs (temperature, blood pressure, heart rate), ECOG performance status, weight. Height at screening only.
- [8] May skip if performed within prior 3 days.
- [9] Symptom-directed and includes vital signs, ECOG performance status, and weight.
- [10] Repeats every 16 weeks ±7 days after week 21.
- [11] Collect serious adverse event information from the time of signed informed consent and nonserious adverse event information from the time of first dose of study drug through 30 days after the last dose or initiation of cytotoxic chemotherapy, a lutamide (bicalutamide, nilutamide, or flutamide), or a new investigational therapy, whichever occurs first. Phone patients for follow-up if they do not come to the clinic.
- [12] Complete, sign, and fax or email the form with requested items to the medical monitor or designee at least 2 business days before the anticipated day 1 visit, if possible. Patient may proceed to day 1 visit when medical monitor or designee approves by signed form or email correspondence.
- [13] Patients with PSA values increased from baseline may discontinue study drug and have safety follow-up unless the investigator considers continuation of study drug to be beneficial.
- [14] Refer to laboratory and imaging instruction manuals for sample processing and imaging acquisition requirements. Interpretation of ¹⁸F-NaF PET/CT imaging performed at the central imaging vendor.
- [15] Collect predose.
- [16] At time of NaF-3.

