5.2.4. Unscheduled Assessments

Unscheduled assessments will be used when deriving baseline and worst case on-treatment for safety and patient-reported outcome analyses (except where noted for baseline ECGs). Additionally, unscheduled assessments will be used for efficacy analyses (eg, defining date of PSA progression, date of last contact).

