Additionally, laboratory results will be programmatically classified according to NCI-CTCAE version 4.0 grade. Non-numerical qualifiers will not be taken into consideration in the derivation of grade (eg, hypokalemia Grade 1 and Grade 2 are only distinguished by a non-numerical qualifier and therefore Grade 2 will not be derived). In summary statistics the number and percentage of patients corresponding to grades that only include non-quantitative criteria will be displayed as a blank or NA (not assessed) rather than 0. If there is any overlap between grade criteria (eg, CTCAE grading criteria for Creatinine Increased – a value can fall into one range based on comparison to ULN and another range based on comparison to baseline), the highest (worst) grade would be assigned to that record. Grade 5 is defined in the CTCAE criteria guidance as an event with an outcome of death. Since laboratory data does not collect an outcome, Grade 5 is not used when programmatically grading laboratory data. Grade 0 or Outside Toxicity Reference (OTR) is not defined specifically by in the CTCAE guidance. However, programmatically this is used as a category to represent those patients who did not meet any of the Grades 1 to 4 criteria. If the laboratory value is evaluable for CTCAE criteria grading (numeric value is present, valid units and ranges are present as required to allow conversion to standard units and grading), and does not qualify for any of the Grade 1-4 criteria for a given lab test, then the value is assigned as Grade 0 or OTR.

Normal ranges will be implemented to identify values that are outside the normal ranges and create the NCI toxicity grade using the CTCAE version 4.0. Parameters that have criteria available for both low and high values will be summarized for both criteria (low and high). Patients will only be counted once for each criterion. The same patient can be counted for both criteria if the patient has laboratory values meeting each criterion. The change from baseline to post baseline value will be calculated for each laboratory parameter where available.

For laboratory parameters that are gradable by the CTCAE, a shift table will be provided for each parameter to summarize baseline toxicity grade versus worst post baseline toxicity grade during the treatment-emergent period. The number and percentage of patients will be provided for each parameter.

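### Protocol 8.4 keeps other-laboratory results from unscheduled and urgent-care visits out of the database, so the SAP's worst-case laboratory outputs cannot include them

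*Protocol*

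**What the plan says.** Protocol 8.4 names one source for safety bloods: "All clinical laboratory safety tests will be performed by the local laboratory specified in Form FDA 1572 Section 4". It then allows a departure: "A different clinical laboratory may be used for unscheduled visits or for urgent care". For results obtained that way, the rule is: "Such laboratory data will not be entered into the study database". The section makes no exception for a severe value, a serious event or a value that leads to stopping drug. Protocol 5.2.7 names toxicity assessment as one reason for an unscheduled visit, and Table 7 lists serum chemistry and hematology among its procedures.

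The SAP relies on such visits. Section 5.2.4 states: "Unscheduled assessments will be used when deriving baseline and worst case on-treatment for safety". Section 6.6.4 then plans:

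- for gradable parameters, a shift table of "baseline toxicity grade versus worst post baseline toxicity grade during the treatment-emergent period";
- for other parameters, a shift table of baseline against the lowest and highest post-baseline result;
- a by-patient listing for patients with grade 3 or 4 values;
- the number and proportion of patients with AST, ALT or total bilirubin above 5 x ULN.

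The liver cut matches one of the laboratory criteria for permanent discontinuation in Protocol 5.3: "AST, ALT, or total bilirubin > 5-times the ULN". On scheduled bloods, footnote 10 of Protocol Appendix 2 says: "Repeats every 16 weeks ±7 days after week 21".

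**The concern.** A worst-case summary is only as complete as the values that feed it. Here, whether a value is captured depends on which laboratory ran the sample, and that choice is plausibly linked to how ill the patient was. Blood taken in urgent care is usually taken because something is wrong. It is therefore a reasonable inference that these results are abnormal more often than routine ones, although the documents give no rate.

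At stake are the completeness of the laboratory outputs and their agreement with the rest of the report. A patient could appear in the disposition and adverse event tables as stopped for raised ALT while the liver summary shows no elevation for him. No SAP rule can repair this afterwards, because the number was never entered.

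**Working it through.** The plan states no figure on this point, so there is none to reproduce. The check traces each kind of result, then shows the direction and scale of a loss.

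**Step 1: where each result goes**

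| Result | Database (Protocol 8.4) | SAP 6.6.4 worst-case outputs | Other record |
|---|---|---|---|
| Scheduled visit, Form FDA 1572 laboratory | Entered | Yes* | Adverse event if a criterion in 8.3.1 is met |
| Unscheduled visit, Form FDA 1572 laboratory | Not barred | Yes*, but not in by-visit statistics | Same |
| Unscheduled or urgent care, different laboratory | Barred | No | Same |

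*Provided that SAP 6.6.4, which restricts summaries to central-laboratory data, is reconciled with Protocol 8.4 and 12, which run safety bloods locally.

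Only the last row is affected.

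**Step 2: direction.** Let S be a patient's entered post-baseline grades and U his barred ones. Then max(S) ≤ max(S and U together). Omitting U can lower the worst grade or leave it unchanged; it cannot raise it. A lost value matters only if no entered value for that patient reaches the same grade.

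**Step 3: scheduled draws.** From Appendix 2, the post-baseline safety bloods to 2 years fall on days 29, 85 and 141, then every 112 days: 253, 365, 477, 589 and 701. That is 8 draws. Protocol 5.4 adds one at safety follow-up, about 30 days after the last dose. A short-lived abnormality between draws would be seen only on unscheduled bloods.

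**Step 4: scale with N = 20.** One patient is 1/20 = 5.0 percentage points. The SAP does not ask for confidence intervals on these outputs; exact (Clopper-Pearson) intervals are used here only to show scale.

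| Patients tabulated | Proportion | 95% CI |
|---|---|---|
| 0/20 | 0% | 0 to 16.8% |
| 1/20 | 5.0% | 0.1 to 24.9% |
| 2/20 | 10.0% | 1.2 to 31.7% |

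**Step 5: illustration under assumptions.** Let p be the proportion of patients with a grade 3/4 value, and q the share of those patients whose only such value came from a different laboratory. The documents give neither. With independent patients:

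- expected number tabulated = 20 × p × (1 − q)
- P(at least one patient missed) = 1 − (1 − p × q)^20

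| p | True expected count | Expected tabulated, q = 10% to 50% | P(at least one missed), q = 10% to 50% |
|---|---|---|---|
| 5% | 1.0 | 0.9 to 0.5 | 10% to 40% |
| 10% | 2.0 | 1.8 to 1.0 | 18% to 64% |
| 20% | 4.0 | 3.6 to 2.0 | 33% to 88% |

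For example, p = 10% and q = 25% give 1 − (1 − 0.025)^20 = 39.7%. The spread across the table shows how little can be said without q.

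**The case against.** **The adverse event route is broad.** A reader might infer that 8.4 removes the evidence for a discontinuation. It does not. Protocol 8.3.1 gives four alternative criteria for treating an abnormal value as an adverse event: it causes signs or symptoms, it needs active intervention, it needs study drug to be interrupted or stopped, or the investigator judges it clinically significant. Any one is enough. A patient taken off drug for an outside ALT result meets the third. Under 8.3.2 the event goes on the adverse event form and, if it leads to permanent discontinuation, on the treatment discontinuation form as well. If treatment emergent, it is tabulated under SAP 6.6.1. The protocol's safety measure of new clinically significant laboratory changes can be captured in part the same way. This objection stands, but it does not put a value into the shift tables, the grade 3/4 listing or the liver summary.

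**The documents do not flatly contradict each other.** SAP 5.2.4 does not promise other-laboratory results, and it works for unscheduled samples run at the Form FDA 1572 laboratory. That also stands. The weakness is that the SAP nowhere says its worst case is limited in this way.

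**The sparse schedule does not measure the loss.** A reader might assume that an abnormality lasts 14 to 28 days, take the 112-day gap, and say that scheduled draws catch only 14/112 = 12.5% to 28/112 = 25%. That describes the longest interval under an assumed duration. The same assumption gives 25% to 50% in the 56-day gaps and 50% to 100% in the 28 days before the day 29 draw. It also ignores the safety follow-up draw. It says nothing about how many unscheduled samples go to another laboratory, which is the quantity that matters here.

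**Other points.** Taken literally, the central-laboratory restriction in SAP 6.6.4 would exclude even the scheduled local values, which is a larger problem for the same outputs. Tying data entry to one laboratory and its reference ranges is a deliberate choice. The study is exploratory, and its primary and secondary endpoints are untouched. These points limit the weight of the issue but do not remove it.

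**Conclusion.** The point holds as a limitation of data capture. If Protocol 8.4 is followed as written, other-laboratory results from unscheduled or urgent-care visits cannot enter the worst-grade shift tables, the grade 3/4 listing or the liver summary. For post-baseline values the effect on the worst case is one-directional, toward apparent safety, and these outputs may disagree with the adverse event and disposition tables.

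The size cannot be estimated, because the share of unscheduled bloods sent elsewhere is not given. What can be said is that each missed patient is 5 percentage points at N = 20. The probabilities in the working rest on assumed p and q and are illustrations only. That outside results are more often abnormal is inference from the purpose of these visits.

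The documents do not support the stronger readings that discontinuations lose their evidence or that most between-visit abnormalities go unrecorded. Severity is minor to moderate.

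**What to change.** 1. Amend Protocol 8.4 so that results from another laboratory for any Table 12 analyte, obtained at an unscheduled or urgent-care visit, are entered with the date, units and that laboratory's reference range. At a minimum, enter those that are grade 3 or 4, that exceed 5 x ULN for AST, ALT or total bilirubin, or that are linked to an adverse event, a treatment interruption or a discontinuation.
2. In SAP 6.6.4, include these values in the worst-grade shift tables, the grade 3/4 listing and the liver summary. Keep them out of the by-visit statistics, as the SAP already does for unscheduled values.
3. In the same revision, reconcile the central-laboratory restriction in SAP 6.6.4 with the local-laboratory rule in Protocol 8.4 and 12. Otherwise step 2 has no effect.

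The cost is one unscheduled laboratory form and a little site data entry. Some outside reports will be incomplete, for example without a reference range, and can be listed without a grade. No extra visits or blood draws are needed. If the protocol is not amended, the SAP and study report should state that the laboratory outputs exclude these results.
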